## g) Specimen Banking

Not applicable.

## h) Data Management and Confidentiality

In **Stages I and II**, each subject will tracked using an Access database. Identifiers and other related information for coordinating research activities (recruitment outcome, research interview call log and interview visit schedule, etc.) will be password

	Protocol Title:	Clinic-based vs. home-based support to improve care and outcomes for older asthmatics
	Principal Investigator Name/Contact Info:	[name], MPH Email: [contact]
	Primary Contact Name/Contact Info	[name]
	Date Revised:	June 13, 2016
	Study Number:	IF1737114, GCO#13-1401, HSM#14-00108

protected and kept on the secure Mount Sinai network drive. Only the PI, project manager, and RAs will have access this database.

Subject	Identifiers in database
Patient	name, MRN, address, phone number, DOB, (social security number, insurer, and beneficiary ID in Stage II only for NYS data on resource utilization)
Caregiver	name, address, phone number, DOB
Clinician	name, address, phone number, email address, job title, DOB

**Security Measures:** Several methods will be employed to reduce the risk of breach of confidentiality. A study identification number will be assigned to each subject in the study. The research data collected and stored will have the study identification number and no other identifying information on it. Research data (hard copies) will be stored in a locked file cabinet where the project manager's office is located in the Center for Advanced Medicine (CAM) Building at [name]. The consent forms and the de-identified study data will be kept in a separate locked file cabinet at the same location. Using this method, if someone were to gain illegal access to the locked filing cabinet with study data, they would have no way to link this data to any identifying information.

Audiotape data access will be limited to only the PI, project manager, RAs and DSMB representatives. The RAs will set up and collect the audio-recordings at each taped session. The recording will be brought from the session directly to the project manager's office at Mount Sinai. It will be stored in a locked cabinet in the project manager's office. Data will be downloaded weekly from the recording device will be kept on the project manager's computer using an encryption software (TrueCrypt) to further ensure the safety of the audiofiles. De-identified transcripts will be sent to one of our partner organizations (Northwestern University, Chicago, IL) for coding and analysis.

### i) Provisions to Monitor the Data to Ensure the Safety of subjects

The Data Safety and Monitoring Plan (DSMP) for **Stage I** activities is described below. The Data Safety and Monitoring Board (DSMB) for the study will be formed before the RCT begins in **Stage II**.

#### Data Safety and Monitoring Plan

A) Monitoring Entity: [name] will be responsible for the data safety and monitoring for the entire study; he will also oversee the safety and monitoring of data collected at ISMMS. [name] will be responsible for the safety and monitoring of data collected at IFH.

	Protocol Title:	Clinic-based vs. home-based support to improve care and outcomes for older asthmatics
	Principal Investigator Name/Contact Info:	[name], MPH Email: [contact]
	Primary Contact Name/Contact Info	[name]
	Date Revised:	June 13, 2016
	Study Number:	IF1737114, GCO#13-1401, HSM#14-00108

Data collected at ISMMS and IFH will be sent for transcription. Transcribed focus groups will be sent to and summarized by Northwestern University. [name] will oversee the data safety and monitoring of the data at Northwestern University.

B) Procedures for Monitoring Study Safety: 1) Safety reviews: The principal investigator will review the safety and progress of this study on a monthly basis. 2) Annual review: The principal investigator will review this protocol on a continuing basis for subject safety and include results of the review in the annual progress reports submitted to the safety officer and the Institutional Review Board. 3) Annual report: The annual report will include a list of adverse events. The annual report will address: a) whether adverse event rates are consistent with pre-study assumptions; b) reason for dropouts from the study; c) whether all participants met entry criteria; d) whether continuation of the study is justified on the basis that additional data are needed to accomplish the stated aims of the study; and e) conditions whereby the study might be terminated prematurely. 3) Institutional Review Board review: The Institutional Review Board will review each protocol annually for safety.

[name] will be responsible for monitoring and reporting safety data from all study sites (ISMMS, IFH, and Northwestern University). [name] will supervise the collection and reporting of safety data for all participants enrolled at IFH. Adverse events will be reported to the ISMMS and IFH IRBs. Additionally, safety data from IFH will be sent to ISMMS monthly. These data will be summarized individually and then combined with Mount Sinai data for reporting to the IRB and PCORI as necessary. Safety data from both study sites will be discussed monthly during study meetings with investigators from all study sites. We have used similar procedures in our prior studies conducted at ISMMS, IFH and Northwestern University.

In addition, we will use encryption software (Truecrypt, TrueCrypt Foundation) to protect all electronic audio data collected at ISMMS. Audio files from ISMMS and IFH will be sent for transcription and the transcripts will be sent to Northwestern University. Northwestern will serve as the Data Coordinating Center.

### j) Withdrawal of Subjects

Patients are withdrawn from the study when they are found to be ineligible or become ineligible after enrollment. When patients are withdrawn, they are still followed up with research interviews, and also with the intervention (if the subject had been randomized to an intervention arm), but their data is later on excluded from analysis.

### 6) Risks to Subjects

	Protocol Title:	Clinic-based vs. home-based support to improve care and outcomes for older asthmatics
	Principal Investigator Name/Contact Info:	[name], MPH Email: [contact]
	Primary Contact Name/Contact Info	[name]
	Date Revised:	June 13, 2016
	Study Number:	IF1737114, GCO#13-1401, HSM#14-00108

Participation in the study poses minimal risk of psychological, social and economic harm. Informing subjects in advance that they may decline to answer any question asked during the interview will mitigate any risks associated with expressing their opinions (e.g., feeling uncomfortable). They will also be assured they can terminate their participation in the study at any time without penalty.

Greater than minimal risk is expected for subjects in the RCT. Participants enrolled into the intervention arms of this study are expected to benefit, having better asthma control. While participants in the usual care arm of this study may not benefit directly from their participation, we anticipate results from this study to benefit future patients by expanding research on comprehensive models of chronic care, including the multidisciplinary management of chronic diseases and the medical home concept.

There always exists, the potential for loss of private information; however, there are procedures in place to minimize this risk. Procedures include: regular quality control data checks, encryption of data, and adherence to the ISMMS policy on data safety and transfer.

## 7) Provisions for Research Related Injury

This research involves minimal to no risk for subjects. The investigators on this project will make themselves available to meet with any participants expressing medical or psychological distress while being interviewed.

In order to reduce the risk of subjects:

1. *Psychological distress may be provoked by issues discussed during the intervention sessions.*  
In order to reduce the risk of subjects becoming psychologically distressed, subjects will be asked at the time of consent to inform a member of the research staff if at any point during the study they feel that participating in the research is causing them undue distress. Subjects will also be clearly instructed at each study visit that they are free to discontinue their participation in the research project at any time and that this will have no consequences at all for their continued medical care. Additionally, if study personnel find that the subject requires referral for mental health services (e.g., suicidal ideation) during the course of the intervention, the study personnel will contact the subject's PCP directly to arrange for referral to mental health services. The IMA clinic has mental health professionals in place to address any distress that is brought on during the interview questions. The costs associated with these services will be included as a part of usual care in IMA.
2. *Violation of participant confidentiality is always a potential risk in research where identifiable data is collected.*  
We have measures and protocols in place to deter the loss of identifiable data. See #5h.

## 8) Potential Benefits to Subjects

	Protocol Title:	Clinic-based vs. home-based support to improve care and outcomes for older asthmatics
	Principal Investigator Name/Contact Info:	[name], MPH Email: [contact]
	Primary Contact Name/Contact Info	[name]
	Date Revised:	June 13, 2016
	Study Number:	IF1737114, GCO#13-1401, HSM#14-00108

While subjects may not benefit directly from their participation, we anticipate results from this study to benefit future older asthmatic patients by improving standard care and physician-patient communication about asthma. Clinician subjects may help improve their work environment by assisting with the design and enhancement of the EMR decision support tools to be available to clinic staff in **Stage II** of the study.

## 9) Provisions to Protect the Privacy Interests of Subjects

Subjects will be informed that their data is confidential. Subjects may stop participation at any time or skip any question if he/she feels uncomfortable.

Throughout the study, steps will be taken to ensure the privacy of participants. The research personnel will not provide details of study to subjects in public waiting areas but will instead disclose details in one of the private exam rooms of the clinic. The research personnel will communicate with subjects through the contact numbers they provide and will not reveal PHI in voicemail messages.

To ensure that subjects feel at ease throughout the interviews and intervention sessions, the research personnel will remind the subjects that if at any point he/she becomes frustrated or does not wish to answer a particular question or participate in an activity or discussion, he/she does not have to do so. In addition, the research personnel will give opportunities for breaks throughout the interviews and sessions.

## 10) Economic Impact on Subjects

Not applicable.

## 11) Payment to Subjects

Subjects enrolled in **Stage I** study activities (focus groups, cognitive interviews) will be reimbursed for their time and effort at each interview with \$25 in cash (\$25 total). Participating SLR staff will not receive monetary compensation; they will be provided with refreshments at the session. Subjects enrolled in Stage II study activities (research interviews at baseline, 3-months, 6-months, and 12-months) will be compensated for their time and effort at each interview.

Subject	Research Interview	Payment	Form of Payment
Patient	baseline	\$ 25	cash at close of interview
	3-month	\$ 10	money order mailed within 2 weeks
	6-month	\$ 15	money order mailed within 2 weeks

	Protocol Title:	Clinic-based vs. home-based support to improve care and outcomes for older asthmatics
	Principal Investigator Name/Contact Info:	[name], MPH Email: [contact]
	Primary Contact Name/Contact Info	[name]
	Date Revised:	June 13, 2016
	Study Number:	IF1737114, GCO#13-1401, HSM#14-00108

12-month	\$ 25	cash at close of interview
----------	-------	----------------------------

## 12) Consent Process

Waiver of HIPAA Authorization: Waivers of HIPAA Authorization from both Mount Sinai and SLR are requested to identify subjects (patients) prior to enrollment into the study.

Waiver of Written Documentation of the Consent Process (Mount Sinai Focus Groups only): A waiver of written documentation of the consent process is requested for the focus group participants. The written script of the information to be provided orally and all written information to be provided include all required and appropriate additional elements of consent disclosure. The research presents than minimal risk of harm to subjects. The research involves no procedures for which written consent is normally required outside of the research context.

The only record linking the subject and the research would be the signed document. The group will be consented together and each participant will be afforded the opportunity to step aside from the group to ask questions.

Setting: Consent will be obtained in a private room at one of the participating Mount Sinai practices or in the patient's home.

Process: We will follow the Informed Consent Process Standard Operating Procedure (SOP) as described in the PPHS document HRP-090. Informed consent will be viewed as a process, i.e. at several times during review of the IRB approved consent document, the subject will be asked to explain in his/her own words what his/her understanding of the consent. This will enable the research personnel to enter into a dialogue with the subject and ensure that the subject understands that he/she is free to withdraw at any time without penalty. Information will be provided to the subjects in terms that they can fully understand. There will be no exertion of any overt or covert coercion. The consent document is written in language that the potential subject can understand. Subjects will be asked to explain the purpose of the study and the expectations of their participation in their own words. They will be encouraged to ask questions prior to giving consent. Prior to signature of the informed consent document we ask the research patient to complete a set of questions designed to assess the patient's essential understanding of the information contained in the informed consent document and given during the informed consent process.

## 13) Process to Document Consent in Writing

We will use the PPHS consent template.

## 14) Vulnerable Populations

 Mount Sinai	Protocol Title:	Clinic-based vs. home-based support to improve care and outcomes for older asthmatics
	Principal Investigator Name/Contact Info:	[name], MPH Email: [contact]
	Primary Contact Name/Contact Info	[name]
	Date Revised:	June 13, 2016
	Study Number:	IF1737114, GCO#13-1401, HSM#14-00108

Include	Exclude	Vulnerable Population Type
	✓	Adults unable to consent
	✓	Individuals who are not yet adults (e.g. infants, children, teenagers)
	✓	Wards of the State (e.g. foster children)
	✓	Pregnant women
	✓	Prisoners

## **15) Multi-Site Human Research (Coordinating Center)**

Northwestern will serve as the Data Coordinating Center for Stage I activities. Audio files from ISMMS, SLR and IFH will be sent for transcription and the transcripts will be sent to Northwestern University.

## **16) Community-Based Participatory Research**

Not applicable.

## **17) Sharing of Results with Subjects**

Not applicable.

## **18) IRB Review History**

## **19) Control of Drugs, Biologics, or Devices**

Not applicable.

## **20) Control of Drugs, Biologics, or Devices**

*Note: The IDS has its own forms that must be completed and a review process that must be followed before the IDS representative will sign off on Appendix B for submission to the PPHS.*

Clinic-based vs home-based support to improve care and outcomes for older asthmatics Statistical Analysis Plan

PI: [name], MPH

NCT02316223

Document Date: June 13, 2016

DATA ANALYSIS (Months 10-36)

a Analysis Plan A HIPAA waiver will be obtained to use de-identified data to compare non-participants (available from recruitment lists) to participants on age, gender, and ethnicity. Assessment of Measurement Invariance: We will examine whether measures are invariant across language and racial/ethnic groups. Measurement invariance will be assessed with MIMIC models or with a method adopted from Rasch analysis for small group sizes.²³² The baseline characteristics of enrolled patients will be compared across the 3 study arms using a chi-square test or ANOVA, as appropriate. We will assess the distribution of the dependent variables as well as other statistical assumptions and apply transformations as necessary.

c Aim 2 Analyses. These analyses will assess whether the CHW intervention may be more suited for a subset of elderly asthma patients. Specifically, we hypothesize that minority patients with psychosocial issues, functional or cognitive impairment will benefit more from a CHW compared to an ACC-based intervention. Functional impairment will be defined as 1 or more dependency with instrumental activities of daily living, in other words, whether the individual requires assistance with housework, food preparation, shopping for groceries or clothing, using a telephone, managing medications, and or managing money.²²⁷ Cognitive impairment will be defined as a mini-mental status exam score of ≤ 27 ;²³⁵ depression as a PHQ-9 score of ≥ 15 (moderately severe);¹⁹⁸ serious and persistent mental illness as having a current or past diagnosis of schizophrenia, schizoaffective disorder, or bipolar disorder; problematic alcohol use as 4 or 5 at one time in the past year for women and men, respectively;²³⁶ and, substance abuse as any current use of an illegal drug or prescription drug used for non-medical purposes.²³⁰ Later exploratory analyses will involve testing other thresholds for these measures. We will limit the analyses to the primary outcomes and compare them between the ACC vs. CHW arms. Hypothesis testing will be based on the final model for ACQ and AQLQ scores, resource utilization and adherence rates described above. We will add an interaction term between treatment arm (ACC vs. CHW) and the factor of interest (i.e., psychological issues, functional or cognitive impairment). The significance of the beta coefficient for the interaction term will be used to assess if the CHW intervention may be more beneficial for these subgroups.

Sample Size Calculation for Aim 2. The expected number of individuals with psychological issues, functional or cognitive impairment was estimated based on data from our cohort study of asthma in the elderly.^{14,49,67,235} We calculated the power of the study to identify whether the regression coefficients for the association between intervention arm and ACQ/AQLQ scores will be different for patients with vs. without substance abuse or functional or cognitive impairment (equivalent to testing the interaction between treatment arm and presence or absence of these conditions). These analyses showed that with 150 subjects per arm, the study will have an >80% power to detect a difference ≥ 0.5 units between the slopes of patients with and without these conditions.

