Asthma history	
 
• Age of onset
 
• Intubations
 
• Current asthma medication use
 
	Interviewer administered at baseline
Smoking history	
 
• NHANES items
 
	Interviewer administered at baseline, 12 months
Cognitive function	
 
• Montreal Cognitive Assessment (MoCA)
 
	Interviewer administered at baseline
General health	
 
• SF-1 general health measure
 
	Baseline, 3, 6, 12 months
Co-Morbidities		From EMR abstraction at baseline
Medications currently used		From EMR abstraction at baseline
Depression	
 
• NIH PROMIS Measures for Depression
 
	Interviewer administered at baseline, 6, 12 months
Anxiety	
 
• NIH PROMIS Measures for Depression
 
	Interviewer administered at baseline, 6, 12 months
Physical functioning	
 
• Activities of daily living
 
• Instrumental activities of daily living
 
	Lawton and Brody

- **Statewide Planning and Research Cooperative System (SPARCS) Data.** The researchers will also access data on patients' healthcare use (including: hospitalizations or emergency department visits at hospitals other than Mount Sinai) from the New York State Department of Health's SPARCS data. Please note that all the SPARCS data collected is for research purposes only, and not clinical care.
- **Assessment of Acceptance and Implementation of Intervention.** In the final stages of the program, we will perform qualitative and quantitative assessments of provider acceptance, use, and implementation of the EMR-based decision support and tools,

	Protocol Title:	Clinic-based vs. home-based support to improve care and outcomes for older asthmatics
	Principal Investigator Name/Contact Info:	[name], MPH Email: [contact]
	Primary Contact Name/Contact Info	[name]
	Date Revised:	June 13, 2016
	Study Number:	IF1737114, GCO#13-1401, HSM#14-00108

provider experience communicating with ACCs and CHWs and vice versa, and patient experiences.

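### SAP Aim 2 defines cognitive impairment and depression on instruments the protocol does not list, names no listed source for alcohol or drug use, and plans no test of the severity hypothesis

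*SAP*

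**What the plan says.** SAP section c (Aim 2 Analyses) asks whether some patients benefit more from the home-based arm (CHW) than from the clinic-based arm (ACC). It defines the modifiers as follows:

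- **Cognition:** "Cognitive impairment will be defined as a mini-mental status exam score of" 27 or less.
- **Depression:** "depression as a PHQ-9 score of" 15 or more.
- **Alcohol:** "problematic alcohol use as 4 or 5 at one time in the past year", with the lower count for women and the higher for men.
- **Drugs:** "substance abuse as any current use of an illegal drug or prescription drug used for non-medical purposes".
- **Serious mental illness:** a present or past diagnosis of one of three named disorders.
- **Functional impairment:** at least one dependency in instrumental activities of daily living (IADL).

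The test is an interaction between arm and "the factor of interest (i.e., psychological issues, functional or cognitive impairment". On outcomes, the SAP says: "Hypothesis testing will be based on the final model for ACQ and AQLQ scores, resource utilization and adherence rates described above". It adds: "Later exploratory analyses will involve testing other thresholds for these measures".

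The protocol's Other Measures table (section 5f, Stage II) lists, for cognition, the "Montreal Cognitive Assessment (MoCA") at baseline and, for depression, an NIH PROMIS measure at baseline, 6 and 12 months. It also lists IADL, smoking items and co-morbidities abstracted from the EMR. The protocol's Aim 2 hypothesis (section 1) expects greater home-based benefit in patients with more severe asthma, and in those likely to miss appointments because of impairment or psychosocial problems, with substance abuse given as an example.

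**The concern.** Both documents are dated June 13, 2016, so this is not a later plan catching up with an older protocol. A mini-mental cut-off cannot be applied to a MoCA score, nor a PHQ-9 cut-off to a PROMIS score. Neither document gives a conversion or a replacement threshold. Whoever runs Aim 2 will have to write new definitions of cognitive impairment and depression. If that happens after outcomes by arm are visible, the choice can follow the result.

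Two further gaps bear on the same aim. The alcohol and drug definitions need a per-occasion drinking count and a report of current drug use, and the measures tables show neither. The modifier named first in the protocol hypothesis, asthma severity, has no planned test. Aim 2 is one of the trial's two aims.

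**Working it through.** **Step 1. Set each SAP modifier against the protocol's measures tables (section 5f).**

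| SAP modifier | SAP basis | Listed in protocol | Result |
|---|---|---|---|
| Cognition | Mini-mental, 27 or less | MoCA, baseline | Conflict |
| Depression | PHQ-9, 15 or more | PROMIS depression, baseline | Conflict |
| Alcohol | Per-occasion count, past year | No item | Source not listed |
| Drug use | Any current use | No item | Source not listed |
| Serious mental illness | Diagnosis | EMR co-morbidities, not itemised | Plausible source |
| Function | One or more IADL dependencies | IADL, no time point shown | Match |

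**Step 2. Severity.** The SAP's Aim 2 analysis and Aim 2 sample size paragraphs do not mention severity. The nearest term is baseline control status in the Aim 1 model (SAP section b). It enters as a fixed main effect, which adjusts the outcome level but does not test whether the ACC-versus-CHW difference varies with severity.

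**Step 3. Count the affected tests.** The SAP names four outcomes: ACQ, AQLQ, resource utilization and adherence.

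- *Three factors (psychological, functional, cognitive):* 3 × 4 = 12 tests. The cognitive factor is affected directly, and the psychological factor through its depression item: 2 × 4 = 8 of 12.
- *Six separate factors (the rows above):* 6 × 4 = 24 tests. The instrument conflict covers cognition and depression: 2 × 4 = 8 of 24. Alcohol and drug use add 2 × 4 = 8 whose status depends on whether a source exists.

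The SAP does not say which structure applies. The three-factor reading is the more natural, because the three factors follow an i.e. and the sample size paragraph repeats them.

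**Step 4. Side check on the stated power.** The SAP claims more than 80% power for a difference of 0.5 with 150 per arm, but gives neither prevalence nor SD for Aim 2. I assume the Table 5 SDs (0.4 for ACQ, 0.3 for AQLQ), two-sided 0.05 and no clustering or dropout. With subgroup prevalence p:

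SE = SD × √(2 / (150 × p × (1 − p))); power = Φ(0.5/SE − 1.96).

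- SD 0.4, p = 0.05: SE = 0.212, power = Φ(0.40) = 0.66.
- SD 0.4, p = 0.10: SE = 0.154, power = Φ(1.29) = 0.90.
- 80% power is reached for p from 7.2% to 92.8% (SD 0.4), or from 3.9% to 96.1% (SD 0.3).

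The claim is attainable under these assumptions. It cannot be confirmed, because prevalence is not stated and, for cognition, will depend on the new definition.

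**The case against.** The strongest defence is that much of Aim 2 can be run. The functional definition matches a listed measure and has a fixed threshold. EMR co-morbidities could supply serious mental illness and perhaps coded substance-use diagnoses. The baseline questionnaire is not among the documents, so alcohol and drug items may exist. The SAP also restates the Aim 2 hypothesis without severity, which could be a deliberate narrowing. All of this stands, but it leaves the two instrument conflicts untouched. A deliberate narrowing would still need to be stated, because the protocol hypothesis is unchanged.

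Several stronger readings are tempting and are not supported:

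- *Alcohol and drug use are not collected.* The documents show only that they are not listed.
- *The main Aim 2 test leaves cut-offs open to search.* The SAP labels the trial of other thresholds as later and exploratory. The risk lies in the missing main definitions for MoCA and PROMIS, not in that sentence.
- *Two thirds of the tests fail on any reading.* That would add the alcohol and drug tests, whose source is only unlisted, to those with a shown conflict. With separate factors the shown conflict is one third (8 of 24).
- *The mismatch inflates false positives.* The number of tests would be the same with matched instruments. The SAP plans a Bonferroni correction in section b, though it does not say whether this reaches Aim 2.

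**Conclusion.** The point holds. As written, the cognition and depression modifiers cannot be built from the data the protocol lists, and the severity part of the Aim 2 hypothesis has no pre-specified test. The shown instrument conflict affects 8 of 12 tests under the three-factor reading or 8 of 24 under the six-factor reading; in the latter, 8 more turn on whether an alcohol and drug source exists. These counts assume the four outcomes named in the SAP, and leave aside the separate question of ACQ in the SAP against ACT in the protocol.

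Confidence is high for the instrument conflict and the missing severity test. For alcohol and drug use the finding is limited to the lack of a listed source. A reader might infer from the missing prevalence that the power claim is false; the check above does not support that. The matter should be corrected, and it can be settled in the SAP before any analysis by arm.

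**What to change.** Before any analysis by arm:

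1. Define cognition on baseline MoCA and depression on baseline PROMIS depression, either as continuous scores or with cut-offs fixed in advance. Keep other thresholds as the labelled exploratory analyses. Keep the IADL definition and confirm that it is collected at baseline.
2. Name the form or EMR field that supplies alcohol and drug use, or drop those modifiers. State whether the psychosocial items form one factor or several.
3. Add one ACC-versus-CHW interaction with a severity variable fixed in advance from listed baseline data, or state that the severity hypothesis is not tested. One option is any asthma ED visit or hospitalization in the 12 months before enrolment, from SPARCS. Its drawbacks: it is a proxy for severity, it overlaps the baseline of the utilization outcome, and it may be tied to site, because the acute care report in protocol section 5a is run at Mount Sinai but not at St. Luke's.
4. Restate the Aim 2 power with the prevalence and SD assumed under the final definitions.

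The cost is SAP rewording and a re-run of one power calculation. MoCA, PROMIS depression and the SPARCS look-back are already listed, so they need no new data collection. The downsides are one added modifier (four more tests) and the possible loss of the alcohol and drug subgroups.

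### Aim 2 tests cognition, depression and IADL only as yes/no factors: a continuous-score interaction would use the data better if benefit is graded, and two of the cuts do not fit the listed instruments

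*SAP*

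**What the plan says.** SAP section c (Aim 2 Analyses) defines three moderators by cutting a score:

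- Function: "Functional impairment will be defined as 1 or more dependency with instrumental activities of daily living".
- Cognition: "Cognitive impairment will be defined as a mini-mental status exam score of ≤ 27".
- Depression: "depression as a PHQ-9 score of ≥ 15 (moderately severe").

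The remaining factors (serious mental illness, alcohol, substance use) are defined by a diagnosis or by use, and this point leaves them aside.

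The outcomes are four: "Hypothesis testing will be based on the final model for ACQ and AQLQ scores, resource utilization and adherence rates described above". The decision rule is the interaction of arm with the factor: "The significance of the beta coefficient for the interaction term will be used to assess if the CHW intervention may be more beneficial for these" (the sentence ends by naming the subgroups). No analysis of any score as a continuous variable is mentioned. The section then adds: "Later exploratory analyses will involve testing other thresholds for these measures". It does not say how many thresholds, which ones, or under what error control. The Bonferroni sentence stands in section b, for Aim 1; section c does not refer to it.

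The paragraph on sample size for Aim 2 treats each condition as present or absent and states that "with 150 subjects per arm, the study will have an >80% power to detect a difference ≥ 0.5 units between the slopes" of the two groups. It prints neither a prevalence nor an SD.

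The Other Measures table in Protocol section 5f lists, for cognition, the "Montreal Cognitive Assessment (MoCA") at baseline. For depression it lists the NIH PROMIS measures at baseline, 6 and 12 months. For physical functioning it lists ADL and IADL scales, with no time point given.

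**The concern.** A cut score treats patients on either side of the boundary as opposites and all patients on the same side as alike. If the advantage of home over clinic support grows gradually with impairment, the yes/no test discards part of the signal. Aim 2 uses two of the three arms and asks for a difference between differences, so lost information matters there. Trying further thresholds on the same data adds tests but does not recover what the cut discarded, and the threshold that happens to look best may not replicate.

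The two documents also disagree on the instruments. The MMSE and PHQ-9 cuts cannot be applied to MoCA and PROMIS scores as written. Unless the passages are reconciled beforehand, someone will have to choose cuts for two of the three scored moderators after the SAP was written.

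**Working it through.** **1. The plan's own power figure.** Inputs: 150 per arm, difference 0.5 (SAP, sample size for Aim 2); two-sided alpha 0.05 and ACQ SD 0.4 (SAP section b and Table 5, assumed to carry over to Aim 2). Prevalence p is not stated and is varied. With n per arm,

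SE = SD × √(2 × [1/(np) + 1/(n(1−p))]), power = Φ(0.5/SE − 1.96).

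At p = 10%: SE = 0.4 × √(2 × [1/15 + 1/135]) = 0.154; 0.5/0.154 = 3.25; power = Φ(1.29) = 90%.

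| Prevalence | Power, SD 0.4, n = 150 |
|---|---|
| 5% | 66% |
| 10% | 90% |
| 20% | 99% |

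So the claim of more than 80% fits Table 5 once prevalence is about 7% or more. It cannot be reproduced exactly, because the Aim 2 prevalence and SD are not printed. It also leans on the small SD: at an assumed SD of 0.8, power is 37% to 77% over prevalences of 10% to 50%. That is a question about the SD and not about dichotomising.

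**2. Information kept after cutting.** Assume a normal score and a moderator effect linear in it. The efficiency of the yes/no interaction relative to the continuous one is the squared correlation between score and indicator:

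RE = φ(c)² / [p(1−p)], with c = Φ⁻¹(1−p).

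Evaluable patients in the two arms: 2 × 150 × 0.85 = 255 (15% dropout, SAP section b). The last column is the power left when the continuous test has 80%: Φ(2.80 × √RE − 1.96).

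| Impaired | RE | Loss | 255 × loss | Power left of 80% |
|---|---|---|---|---|
| 50% | 0.637 | 36% | 93 | 61% |
| 20% | 0.490 | 51% | 130 | 50% |
| 10% | 0.342 | 66% | 168 | 37% |

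At 5% impaired the loss is 78%. Protocol section 5c gives a total of 405, although its site numbers add to 175 + 175 + 100 = 450. With 405 there are 135 per arm and 2 × 135 × 0.85 ≈ 230 evaluable patients; the percentages stay the same.

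**3. Skewed scores.** Simulated count distributions (assumed, with the effect still linear) gave losses of 37% to 60% for one or more IADL dependencies, 35% to 48% for PHQ-9 ≥ 15, and 34% to 51% for MMSE ≤ 27. The size does not depend on normality, but it does depend on linearity.

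**4. If the effect is a step at the cut.** The yes/no test then loses nothing. The same squared correlation applies in reverse, so a linear term would keep only RE of the information.

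**5. Trying several thresholds.** Simulated chance of at least one p < 0.05 with no true interaction (one outcome, 127 per arm, cuts spread over the 10th to 50th percentile, 4,000 to 8,000 replicates):

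| Cuts per score | One score | Three independent scores |
|---|---|---|
| 1 | 5% | 14% |
| 3 | 12.5% | 32% |
| 5 | 16% | 41% |

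The SAP names four outcomes, so the opportunities are more numerous than this table shows.

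**The case against.** - *The cuts are fixed in advance and the others are labelled exploratory.* This stands as regards the written plan. A reader might infer that the main Aim 2 tests rest on searched cut-points, but the SAP does not say so. The inflation in step 5 belongs to the exploratory analyses and does harm only if a searched cut is reported as confirmatory. The protection is incomplete, however: for cognition and depression the fixed cut is on an instrument that the protocol does not list.
- *The power is already adequate for the binary factor.* This also stands. A reader might infer that the information loss disproves the stated power above 80%. It does not, because that figure was calculated for presence or absence. The continuous test would use the same patients better if the effect is graded.
- *The loss is hypothetical.* Correct: linearity is a premise, and the documents give no prevalence or distribution. A fixed loss of a third to two-thirds cannot be asserted as fact.
- *Interaction tests are not shown to be the weakest in the trial.* Agreed. Table 5 asks for 510 patients for equivalence on utilization and on adherence, more than the 405 or 450 to be recruited, whereas the ACQ/AQLQ interaction is stated at over 80%.
- *Aim 2 seeks subsets of patients, and named categories answer that directly.* This is a reason to keep the categories as a display. It does not require the test itself to be on the dichotomy, since the estimated difference can be read at any point of the score.

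**Conclusion.** The point holds in a conditional form. Three scored moderators enter Aim 2 only as yes/no factors, no continuous analysis is planned, and the sole follow-on is an unspecified set of other thresholds. If the CHW-ACC difference changes linearly with a roughly normal score, the cost is about 36%, 51% and 66% of the information at 50%, 20% and 10% impaired (93, 130 and 168 of 255 patients, at 150 per arm and 15% dropout). If the effect is a step at the cut, the cost is nil.

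The mismatch of instruments is a plain contradiction between SAP and protocol and needs no assumption. It strengthens the case for the continuous test, which works on whichever instrument is collected and needs no new cut. This is a worthwhile improvement to the analysis, not a flaw that invalidates Aim 2.

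**What to change.** In SAP section c:

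1. Reconcile the cognition and depression instruments with the protocol's Other Measures table, and state that IADL is taken at baseline.
2. For each scored moderator, make the interaction of arm with the continuous baseline score, on the instrument collected, the Aim 2 test: a linear term with a pre-stated check for non-linearity, such as a spline.
3. Show the estimated CHW-ACC difference with its confidence interval along the score. Keep the reconciled named categories as a supporting subgroup display.
4. Keep yes/no coding for factors that are truly binary, such as a psychiatric diagnosis.
5. Either drop the tests of other thresholds, or list the thresholds in advance and report the results as unadjusted and hypothesis-generating.

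The cost is SAP wording; the protocol already lists a scale for each moderator. The drawback is lost power if the true effect is a step at the cut (step 4 of the working). The non-linearity check and the category display would help to reveal such a step, though they would not restore the power of the linear test.
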